## **Qualitative process studies**

There will be two qualitative process studies, one with participants and one with central support facilitators. Interviews in both these studies may be carried out anytime between 2-12 months after participants begin the study. The most important role of these qualitative process studies will be to obtain an in-depth understanding of the perspective of participants and supporters and to reveal any influences on their experience and outcomes of the intervention and trial that had not been anticipated by the research team. Accordingly, all our qualitative research will commence with inductive data collection methods, using openended questions that allow participants to freely describe their experiences and views in their own way, and to focus on whatever is most salient to them. However, to ensure coverage of all potentially relevant aspects of the intervention and its implementation, we will then employ the constructs of our theoretical framework (represented in our logic model) as prompts in our topic guide. The Active Brains intervention logic model will be submitted for publication as part of our intervention planning work, in preparation.

## Qualitative process study with participants

We will interview 12-18 participants from each of the intervention arms, employing purposive sampling to ensure a diverse range of participants in terms of demographic and clinical profiles, as well as website usage. Participants will have consented to be contacted by the research team throughout the study. Participants will be invited to participate by the research team (phone, email or by post) and asked if they would be willing to take part in a telephone interview. Participants will complete a separate consent form (online) prior to taking part in an interview. During the interview, open-ended questions will be used to explore participants' perceptions of the study, the website (if in one of the intervention groups) and the support they received from the central facilitator (if in the support group). Participants in the control group will also be asked about the brief advice they were given at baseline. Participants will be offered a £10 high street voucher as reimbursement for their time and effort.

### Qualitative process study with central support facilitators

The second sub-study will use face-to-face or telephone interviews to explore central support facilitators' views of the study procedures, the website, the training they were provided and the support that they provided to patients (including perceptions of the CARE approach).

## **Analysis**

Data from both qualitative process studies will be analysed, firstly, using inductive thematic analysis to identify themes emerging from and grounded in the data, to ensure that these represent participant perspectives and have the potential to challenge or extend our understanding of the factors and processes operating. Inter-rater agreement will be sought between team members. Following this, we will also examine the ways in which these inductively derived themes map onto, elaborate or diverge from our theoretical frameworks, so as to relate our context-specific insights to generalisable theoretical constructs. The findings will be discussed and interpretations agreed between the co-investigators (including PPI representatives).

#### **Serious Adverse events**

#### **Definitions**

For this study Serious Adverse Event (SAE) is defined as any untoward medical occurrence or effect that at any dose:

- Results in death
- Is life-threatening refers to an event in which the subject was at risk of death at the time of the event; it does not refer to an event which hypothetically might have caused death if it were more severe
- Requires hospitalisation, or prolongation of existing inpatients' hospitalisation
- Results in persistent or significant disability or incapacity
- Other important medical events based upon appropriate medical judgment; they may jeopardise the participant and may require medical or surgical intervention to prevent one of the outcomes listed in this definition.

### Causality

An SAE occurring to a research participant will be reported to the Active Brains study team where, in the opinion of the Principal Investigator at site, the event was related to administration of any of the research procedures, and was an unexpected occurrence. The causality assessment of the event should always be undertaken by a medically qualified doctor who is delegated to do so as indicated on the trial delegation log.

### **Expectedness**

For the purposes of this trial no SAEs are considered expected.

# Non serious AEs and exemptions

- Non-serious AEs will not be collected.
- SAEs NOT DIRECTLY related to the Trial are not required to be reported, this includes deaths and hospital admissions as assessed by PI at site as being not related to the trial website intervention. In such cases deaths will be reported using an End of Study form and will be sent directly to the trial team as per SOP.
- Pre-planned hospitalisation e.g. for pre-existing conditions which have not worsened, elective procedures for a pre-existing condition will not be classed as an SAE unless deemed related to the trial. Hospital admissions that are not directly related to the trial do not need to be reported.

# Reporting

GP Practices will inform the Active Brains Study Team of any SAEs considered to be related to the trial immediately but at least within 24 hours of becoming aware of the event occurring. SAEs should be reported using the trial specific SAE Report Form and completed in as much detail as possible and faxed/emailed to the Active Brains Study Team. Note that the initial report can be made by phone but this must be followed up as soon as possible with a paper report form.

The Active Brains Programme Manager will notify the appropriate REC should an SAE be considered related to the trial and unexpected within 15 days of the receipt of the report.

### Follow Up

All SAEs will be followed up until resolved or an end of trial criteria is met (e.g. patient withdrew from study. All SAEs will also be sent to the PSC.

**Table 2 – List of Measures** 

Measure			Base	eline		Year 1 and Year 5 Year 2, year 3 and follow-up Year 4 follow-up							
		Usual	Active Brains	AB + Support	Cohort	Usual	Active Brains	AB + Support	Cohort	Usual	Active Brains	AB + Support	Cohort
meas g estim ii educa eth	ent Socio Demographic ures: (age, date of birth, ender, postcode (to ate deprivation indices); nternet experience, ation level, work status, inicity, height, weight)	Х	X	Х	Х								
me , fami sm	Clinical/behavioural asures collected from patient report: ily history of dementia b, noking status, alcohol take, BMI, potential dementia status.	X	X	X	X	X	X	X	X				
Н	ealth conditions and medications	Х	Х	Х	Х	X*	X*	X*					
Sel	f-reported respiratory infections					Х	Х	Х	Х				
	COVID-19 status	Χ	Χ	Χ	Χ	Χ	Χ	Χ	Χ				
	ong-COVID status					X	X	X	X	Χ	Χ	Χ	Χ
	of pocket expenditure					X	X	X	Χ				
re sys	ral measures from notes eview (comorbidities, stolic blood pressure, elesterol, frailty score)					X*	X*	X*					
Cognitive Performance Tasks	Primary Outcome: Reasoning (measured using the Baddeley reasoning test [47, 57])	X	X	X	X	X	X	Х	X	X	X	X	X
Cognitive P	Spatial Working Memory (measured using the Self ordered search test)	Х	Х	Х	Х	Х	Х	Х	Х	Х	Х	Х	Х

	Digital Vigilance	Χ	Х	Х	Χ	X	Х	Χ	X	Х	Χ	Х	Х
	(attention - measured												
	using the 'digit' span												
	task [58])												
	Verbal Short-term	Χ	Х	Х	X	Х	Х	X	X	Х	Χ	Χ	Χ
	memory (measured												
	using the paired												
	associates learning												
	[59])												
	ied version of IQCODE	Χ	Х	Х	Х	Х	Х	Х	Х	Х	Χ	Х	Х
	allow self-report)												
	mental Activities of	Χ	Χ	Χ	Χ	Χ	X	Χ	Х	Χ	Х	Χ	Χ
	living [54]												
The p	atient Enablement					Х	X	Х	X				
Scale													
Intern	ational Physical Activity	Х	Х	Х	Х	Х	Х	Х	Х	Х	Х	Х	Х
	tionnaire (IPAQ) plus												
	gth and balance items												
[61]													
	ty of Life (EQ5D) [55]	Χ	Х	Х	Х	Χ	Х	Х	Х	Х	Х	Х	Х
	MWBS [62]	X	X	X	X	X	X	X	X				
SF12		X	X	X	X	X	X	X	X				
	nosis of dementia					X*	X*	X*					
Diagil	iosis of defficitia					^	_ ^	^					
Morta	dity					Χ*	Χ*	Χ*					
IVIOITA	inty					_ ^	_ ^	_ ^					
Health	h economic analysis of					Χ*	Χ*	Χ*					
	effectiveness will require					_ ^	^	_ ^					
	rce usage (meds,												
	ultations, hospitalisation,												
	attendance, outpatient												
visits)	 												
	ry behaviour (food	X	X	Х	Х	Х	X	Х	X	X	Х	Х	Х
	ency questionnaire, with												
the ac	ddition of 2 items about												
nuts a	and oils) [64]												
Brain	training behaviours					Х	Х	Х	Х	Х	Х	Х	Χ
	nt rated adherence to						Х	Х	Х				
	ges in behaviour and list												
_ ~	riers they felt												
	buted to their												
	ence (measured with												
	ETS questionnaire) [65]												
	Geriatric Depression	Х	Х	Х	Х	X 	X 	X 	X 				
	[66, 67]	^	^	^	^	^	^	^	^				
	efficacy for exercise	Χ	Х	Х	Х	Х	Х	Х	Х				
	-	^	^	^	^	^	^	^	^				
scale	S Social Support	Χ	Х	Х	Х		-						
	• •	٨	^	^	^								
Surve	ey – 8 item [69, 70]												

Social Support for Exercise scale [71]						Х	Х	Х				
Locus of Causation in	Х	Х	Х	Х	Х	Х	Х	Х				
Exercise [72]												
Technology Acceptance						Χ	Χ	Χ				
Model Perceived Ease of												
Use scale [73-75]												
Pedometer use/purchase					X	X	Х	X				
Objective patient data												
Usage of the Active Brains		Χ	Х	Х		Х	Х	Х		Х	Χ	Х
website throughout (including												
what components viewed												
and any data entered online												
such as at goal reviews).												
Objective supporter data												
Supporters' Usage of Active			X				Х				Χ	
Brains website (throughout												
study)												
Emails sent to participants			X				Х				Χ	
throughout study												
Qualitative data												
Interviews with patients about					Xa	Xa	Xa					
their experiences of the study												
and/or intervention												
Interviews with Central						)	X					
Support Facilitators about												
their experiences of the study												
and intervention												
Proxy-Measures (not cohort	group						4	_	1	.,	0.4	
		Bas	seline			Years	1 and	5		Year	s 2-4	
Informant Questionnaire on												
Cognitive Decline in the							X					
Elderly (IQCODE) (short												
form) [56]												
Quality of Life (EQ5D5L-												
proxy version 2) to be						2	Χ					
completed by the nominated						•						
contact person (if necessary)												
IADL proxy version to be												
completed by the nominated							Χ					
contact person (if necessary)						-						

\*=notes a measure collected at notes review at Year 1 **or** 5 (depending on when notes review conducted).

[figure not shown]
<sup>1 = collected at year one only (not year five also)

<sup>a = Year 1 only; process interviews to be conducted 2-12 months after commencement of study

b = baseline only

 $^{\rm c}$  =  $\,$  Frailty estimated from IADL and comorbidity data

Figure 1 - Flow of participants through study

#### 1 Introduction

### 1.1 Purpose of Statistical Analysis Plan (SAP)

This statistical analysis plan (SAP) describes in detail the methods that will be used to analyse the data collected as part of the Active Brains trial. This will form the basis of the final trial publication. The final analysis will follow the SAP to ensure that the analyses are conducted in a scientifically valid manner and to avoid post hoc decisions which may affect the interpretation of the statistical analysis. Any deviations from the SAP will be detailed in the final report.

## 1.2 Trial background and rationale (short synopsis)

The prevalence of dementia is estimated to be between five and seven percent amongst those aged over 65 [1, 2] and the absolute number of cases is likely to increase due to people living longer [3]. It has been estimated that if interventions could delay both disease onset and progression by a modest 1 year, there would be nearly 9.2 million fewer worldwide cases of the disease in 2050, with nearly the entire decline attributable to decreases in persons needing a high level of care [3].

Cognitive impairment in the absence of dementia is more common, but prevalence estimates vary considerably depending on definitions [4]. Mild Cognitive Impairment (MCI) is the most commonly used definition, conventionally defined as a deterioration in at least one non-memory cognitive domain in addition to memory impairment, without severe functional impairment or loss of instrumental activities of daily living [4, 6]. An alternative way of characterising cognitive impairment is Age Associated Cognitive Decline (AACD). AACD is defined as one standard deviation (SD) below normal cognitive functioning in any cognitive domain, with some investigators having an additional criterion (self-report of a gradual decline in memory present for at least 6 months) [4].

It is now widely recognised that proactive management of modifiable risk factors can either delay onset or slow progression of dementia [5]. There is mounting evidence that healthy behaviour change (particularly physical activity) and cognitive exercises improve cognitive functioning and activities of daily living. Behavioural interventions are complex and resource intensive if delivered by purely face-to-face methods. In contrast, the internet is now used extensively and successfully by older people for self-management [6, 7]. Although many individuals may benefit from a free standing intervention (without additional support), the additional impact of behavioural facilitation may be important in helping initiate and maintain behaviour change [8, 9] - and the effectiveness and cost-effectiveness of a more intensive intervention may vary with the risk of developing dementia.

The primary aim of this study is therefore to assess the effectiveness and cost-effectiveness of a digital intervention (Active Brains) to help support older adults (60-85 years) with and without cognitive impairment in making healthy changes (physical activity, brain training, diet) to maintain cognitive function and prevent cognitive decline.

#### 1.3 Objectives

Amongst older adults (60-85 years) both with and without cognitive impairment, the primary research objectives are at 1 and 5 years:

- 1. to estimate the clinical effectiveness and cost-effectiveness of the Active Brains digital intervention (compared with usual care) in maintaining cognitive functioning (assessed by verbal reasoning performance).
- 2. to estimate the clinical effectiveness and cost-effectiveness of the Active Brains digital intervention (compared with usual care) in maintaining cognitive functioning (assessed by verbal reasoning performance) when supported as necessary by a trained behavioural facilitator.

At the five-year follow-up point, a further primary objective is to estimate the effectiveness of the Active Brains digital intervention in delaying dementia diagnosis. This will be determined by data collected from patient notes review.

#### **Secondary Research Objectives:**

Secondary research objectives are to evaluate the effectiveness of the Active Brains digital intervention across a number of other key outcomes at 1 and 5 years:

- 1. Instrumental Activities of Daily Living
- 2. Additional cognitive outcomes (including spatial working memory, attention, and verbal short-term memory)
- 3. Health-related quality of life
- 4. Patient enablement
- 5. Depression
- 6. Changes in the target behaviours (physical activity (including sedentary time), healthy eating, engagement with brain training games)
- 7. Mortality data

#### 1.4 Definition of endpoints

A complete list of measures is provided in table 1 at the end of the document. Participants in both the randomised trials and cohort study will be followed-up every 12 months for the five year duration of the study. At years one and five, participants will be asked to complete a full set of follow-up measures. In years two, three and four participants will only be requested to complete a subset comprising the most important outcome measures.

#### 1.4.1 Definition of primary endpoint

The primary outcome is the Baddeley Verbal Reasoning score [10, 11] at 1 year.

The primary outcome at 5 years will be the diagnosis of dementia. The primary definition of dementia diagnosis will be based on diagnosis in the notes. Sensitivity analyses to this definition are provided in section 4.5.9.

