## Non-cognitive decline trial

We assume few of those who have no cognitive impairment at baseline will develop dementia. For the primary outcome of cognitive decline we assume an alpha of 0.05 and 90% power to detect a standardised mean difference of 0.1 in the Baddeley. This requires 2103 per group. Assuming that 60% will be available to provide follow-up within 5 years, that rises to 3505 per group or 10,515 in total.

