#### 4.4 Primary endpoint

The Baddeley verbal reasoning score at 1 year will be analysed using linear regression, adjusting for baseline Baddeley verbal reasoning score and age, gender, IMD score, number of comorbidities and polypharmacy (yes/no). Adjustment for prognostic covariates, specified a priori, is now commonly recommended in the primary analysis of trial data and can potentially increase power [36, 37]. Assumptions for linear regression will be checked using QQ plots for normality and residual vs fitted value plots for linearity and homoscedasticity. If linear modelling assumptions are not met, the data will be transformed using, e.g., a Box Cox transformation and back transformed at values of interest.

The primary analysis will use multiple imputation with chained equations. The imputation model will include all variables in the analysis model and any baseline covariates predictive of

the Baddeley verbal reasoning score or its missingness. Predictors of missingness will be ascertained using Lasso regression [35]. Potential auxiliary variables will include all baseline variables. A model for outcome that includes randomised group, baseline outcome and all potential auxiliary variables will be fitted using the LASSO with 10-fold cross-validation [38]. The regularization penalty (denoted by  $\lambda$ ) will be chosen such that the cross-validation error was within one SE of the minimum [39]. The auxiliary variables that are included in the fitted model from the LASSO will be included in the imputation model for the outcome, i.e., the LASSO will used to select variables for the imputation model but not to estimate parameters of the imputation model. One hundred imputations will be performed and the imputed estimates will be combined using Rubin's rules. Imputation will be performed separately by randomised group and then combined [40].

All tests will be two-tailed with point estimates and 95% confidence intervals for the treatment effect presented. No formal adjustment for multiple significance testing will be applied. Analyses will be performed using Stata version 17 or above.

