## 4.5.10 Diagnosis of dementia

Diagnosis of dementia will be obtained from notes review. This will be analysed using logistic regression, adjusting for the same covariates as in the primary analysis.

The primary definition of dementia will be based on:

1. If there is a notes diagnosis of dementia participants will be classed as having dementia.

As sensitivity analyses, we will use the following methods to ascertain the dementia outcome:

- 2. As recording in notes is suboptimal, consider self-report item "Has a doctor or other medical worker ever said that you have dementia?" (Y/N) this data currently collected in baseline and year 1 and year 5 follow-up online/paper measures.
- 3. Evidence of significant decline in Baddeley (baseline to follow-up) **AND** evidence of functional deterioration (**EITHER**: a) significant change in self-report IQCODE (baseline to follow-up) **OR** b) two self-report questions on difficulty in finance and planning\* (NB the Caerphilly study was based on informant not self-report). Difficulty in finance and planning items collected in year 5 online/paper measures.

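### The SAP's endpoint and analysis sections leave out the continuous Baddeley score at 5 years, although its objectives treat that score as primary and the non-decline trial was sized on it

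*SAP*

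**What the plan says.** **Endpoint definitions.** SAP 1.4.1 gives two statements: "The primary outcome is the Baddeley Verbal Reasoning score [10, 11] at 1 year", and "The primary outcome at 5 years will be the diagnosis of dementia". It adds that "The primary definition of dementia diagnosis will be based on diagnosis in the notes". Neither statement distinguishes the cognitive-decline trial from the non-decline trial. The secondary list in 1.4.2, which covers 1 and 5 years, omits the Baddeley score and includes diagnosis of dementia. Section 1.4.3 places the cognitive measures at years 2 to 4 among the process measures.

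**Analysis.** Section 4.4 says "The Baddeley verbal reasoning score at 1 year will be analysed using linear regression". Section 4.5.2 applies the same approach to the three other cognitive tests. Dementia is analysed in 4.5.10, under the secondary endpoints: "This will be analysed using logistic regression, adjusting for the same covariates as in the primary analysis".

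**Objectives.** SAP 1.3 says of older adults "both with and without cognitive impairment, the primary research objectives are at 1 and 5 years", and what follows is verbal reasoning. Dementia at five years is then added as a further primary objective.

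**Sample size.** For the decline trial, SAP 2.2 calls cognitive decline at 5 years the primary outcome. For the non-decline trial it says "We assume few of those who have no cognitive impairment at baseline will develop dementia", sizes on a Baddeley difference of 0.1 SD with 90% power, and continues: "Assuming that 60% will be available to provide follow-up within 5 years, that rises to 3505 per group or 10,515 in total". In the Protocol's Sample Size Calculations, the 5-year Baddeley figures of both trials stand under a heading that calls them the primary outcome at five-year follow-up.

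**The concern.** The sections that control the 5-year analysis (1.4.1 and 4.4) do not match those that state what the trial is for and how large it must be (1.3 and 2.2).

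In the decline trial the damage is limited. Dementia is the limiting factor for sample size there and has a stated power of 80%, so what is missing is the 5-year Baddeley analysis.

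In the non-decline trial the gap is more serious. Its size rests on the 5-year Baddeley score, yet its only defined 5-year primary is an outcome the SAP expects to be uncommon. Read literally, that trial's formal 5-year result would come from a comparison with no stated power, and the comparison it was enlarged to make would have no SAP model.

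The ambiguity also spreads. Section 4.6.1 repeats the subgroup analyses in the same way on the primary outcome at 5 years, and a reader cannot tell whether that means a linear model of Baddeley or a logistic model of dementia. SAP 1.1 says the plan is there to prevent post hoc decisions. As it stands, what counts as the primary 5-year result could be settled after the data are seen.

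**Working it through.** **Inputs.** SAP 2.2, non-decline trial: difference 0.1 SD, alpha 0.05, power 90%, 60% followed at 5 years. Protocol, non-decline trial: 70% followed at 1 year. SAP 4.4: two-sided tests. SAP 2.2, decline trial: dementia 25% control against 20% intervention, a risk ratio of 0.20/0.25 = 0.8.

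**Step 1: reproduce the plan's own figures.**
- n per arm = 2(1.960 + 1.282)²/0.1² = 2,102. The t-based version gives 2,102.4, rounded up to the plan's 2,103.
- 5 years: 2,103/0.6 = 3,505 per arm; × 3 = 10,515.
- 1 year: 3 × 2,103/0.7 = 9,013.
- Difference: 10,515 − 9,013 = 1,502 participants, recruited because of the 5-year Baddeley calculation.
- With 2,103 evaluable per arm, power for 0.1 SD is 90.0%.

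**Step 2: trace the 5-year Baddeley score through the SAP.**

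| Section | Treatment of the score at 5 years |
|---|---|
| 1.3 Objectives | Primary objective, both populations |
| 2.2 Sample size | Basis of the non-decline trial's size; called primary for the decline trial |
| 1.4.1 Primary endpoint | Absent (1 year only) |
| 1.4.2 Secondary endpoints | Absent |
| 4.4 Primary analysis | Absent (1 year only) |
| 4.5.1 Key secondary | Category change derived from Baddeley, 1 and 5 years, no model stated |
| 4.5.2 Cognitive tests | Absent (other three tests only) |
| 2.5 Final analysis | General promise of a 5-year analysis; no outcome or model named |

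**Step 3: power for dementia in the non-decline trial.** The documents give neither an event rate nor an effect for this trial. I assume the decline trial's risk ratio of 0.8 and vary the control 5-year risk p₁, with p₂ = 0.8p₁ and p̄ their mean.

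Power = Φ{[(p₁ − p₂) − 1.96·SE₀]/SE₁}, where SE₀ = √[2p̄(1 − p̄)/n] and SE₁ = √{[p₁(1 − p₁) + p₂(1 − p₂)]/n}.

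The matching sample-size formula returns the plan's 1,094 for 25% against 20%, so the method agrees with the plan's.

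Example with p₁ = 3%, n = 2,103: p₂ = 2.4%, SE₀ and SE₁ both about 0.00500, (0.006 − 0.00980)/0.00500 = −0.76, and Φ(−0.76) = 22%.

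| Assumed control 5-year risk | 2,103 per arm (60% followed) | 3,505 per arm (all randomised) |
|---|---|---|
| 1% | 10% | 14% |
| 2% | 16% | 24% |
| 3% | 22% | 34% |
| 5% | 35% | 52% |

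For 80% power at 1%, 3% or 5%, the evaluable number per arm would have to be about 35,001, 11,455 or 6,745.

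**The case against.** A reader might infer that the 5-year Baddeley score has no standing at all. The documents do not support that. SAP 1.3 gives it primary-objective status, SAP 2.2 and the Protocol's sample-size headings call it primary at five years, and the SAP's list of measures labels the Baddeley test the primary outcome and schedules it at years 1 and 5.

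A reader might also infer that it would never be analysed. That too goes beyond the text. SAP 2.5 promises a 5-year analysis in general terms. Section 4.5.1 includes a Baddeley-based category change at 5 years, including the move from no impairment to impairment. The Protocol's Statistical analysis section gives linear regression controlling for baseline for the primary outcome, with no limit to 1 year. Absence from 1.4.2 is weak evidence by itself, because that list also omits the key secondary endpoint.

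Nor does the SAP expressly assign dementia as primary to the non-decline trial; 1.4.1 simply does not separate the trials. The Protocol is not uniform either: its objectives name the Baddeley as the one-year measure, and its dementia objective is limited to neither trial.

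Finally, 5-year work depends on the 1-year results, and the 1-year primary is clear and unaffected.

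These points narrow the finding to an inconsistency, but they do not remove it. The category change is not the continuous score used for sizing. The Protocol's general model has neither the covariate set nor the imputation detail of SAP 4.4, so the 5-year analysis is still open to choice.

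**Conclusion.** The point holds as an internal contradiction: SAP 1.4.1 and 4.4 against SAP 1.3, SAP 2.2 and the Protocol's five-year sample-size headings. The continuous Baddeley score at 5 years is missing from the SAP's endpoint definitions and has no SAP-specified model, although 1,502 of the non-decline trial's 10,515 participants are there because of it.

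The stated 90% power belongs to the Baddeley comparison. For dementia in that trial the SAP states none. On the assumptions above it lies between about 10% and 35% with 60% followed, or 14% and 52% if notes review reached everyone. These figures depend on an assumed risk ratio of 0.8 and assumed control risks of 1% to 5%; a higher risk would give more power. They illustrate the problem, while the contradiction itself needs no assumption.

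Two smaller faults belong with it. At 5 years dementia is both primary (1.4.1) and secondary (1.4.2, and 4.5.10 under the secondary endpoints). The references to 4.5.9 for the dementia definition, in 1.4.1 and 2.2, lead to the SF12; the definition is in 4.5.10.

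**What to change.** 1. In SAP 1.4.1, list the Baddeley score at 5 years as a primary endpoint, in line with 1.3 and 2.2, and extend the 4.4 analysis to year 5.
2. State for each trial which 5-year outcome or outcomes are primary, and which one the 4.6.1 subgroup analyses use. If a trial has two, say how they will be read together, since SAP 3.5 makes no multiplicity adjustment.
3. If dementia stays primary in the non-decline trial, say that the trial was not powered for it. Making it secondary there would alter a Protocol primary objective; that is the sponsor's decision and would need more than a SAP edit.
4. Reconcile the primary and secondary listings of dementia at 5 years, keeping its 1-year secondary status. Deleting it outright from 1.4.2 would lose that.
5. Change the 4.5.9 cross-references to 4.5.10.

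The cost is SAP wording and one further run of a model already specified. The Baddeley test is already scheduled at year 5, so no data collection is added and no sample size changes. It should be done before any 5-year data are seen.
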